Supporting this favorable assessment, a substantial body of research not only confirms the safety of exercise but also endorses the significance of physical activity and lifestyle changes in cancer management. This evidence base, coupled with medical endorsement of physical activity for enhancing survivor outcomes, bolsters confidence in the trial's approach.

To ensure ongoing safety and integrity, risks and benefits will be continuously assessed, adjusting protocols as necessary to safeguard participant well-being. This trial aligns with best practices in cancer treatment and reflects a commitment to advancing survivor care through evidence-based lifestyle interventions.

Section 3: TRIAL OBJECTIVES, ENDPOINTS AND ESTIMANDS

Trial Objective 1: Impact on Total Healthcare Expenditure

Clinical Question: Does participation in Complement Theory's 24-week Live 1:1 Coaching program, focusing on Exercise and Meditation and supplemented with evidence-based information on Diet, Sleep, and other lifestyle practices, adjunct to the core treatment, lead to a reduction in total healthcare expenditure for cancer survivors?

- Endpoint(s): Total healthcare expenditure, including hospitalization costs, medication expenses, outpatient visits, and any other related healthcare services that we planned and unplanned, cancer and non-cancer, over the trial period.
- Estimand(s): The difference in mean total healthcare expenditure between the intervention and control groups over a specified period (e.g., at 3, 6, 12 months and 18 months from baseline).

Trial Objective 2: Influence on Adherence to Treatment

Clinical Question: How does participation in Complement Theory's program affect adherence to treatment?

- Endpoint(s): Measured through change in MMAS-8 survey scores
- Estimand(s): The mean difference in change in Adherence scores between the intervention and control groups at specified time points during and after the intervention period.

Trial Objective 3: Influence on Quality of Life Score (QoLS), Physical Activity, Sleep Quality and Pain Levels

Clinical Question: How does participation in Complement Theory's program affect Quality of Life, Physical Activity, sleep quality and Pain levels in cancer survivors compared to those receiving standard care?

- Endpoint(s): Measured through change in FACT-G, GLTEQ, BPI-ShortForm, PROMIS scores which are designed to assess various dimensions of quality of life, physical activity levels, pain levels and sleep quality.

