6.1 Schedule of Events

Schedule of events for test/treatment group:

		Week	Week	Month 1-6	Month 7-18
Intervention or Assessment (Test)	Baseline (Day -30 to -1)	1/3/5/7/9/11/13/15/17/19/21/23	2/4/6/8/10/12/14/16/18/20/22/24	(Every 30 days)	(Every 30 days)

Live 1:1 Lifestyle Coaching - 3-5 days per week, 45 mins each		X	X		
Async access to Lifestyle modification content curated by CT		X	X		
Informed Consent	X				
Eligibility Criteria Assessment	X				
Demographic Details	X				
EHR Access Consent	X				
Claims Data Access	X		X		X
QoLS (FACT-G Form)	X		X		X
Weight	X		X		X
Physical Activity (GLTEQ)	X		X		X
Pain (BPI-ShortForm)	X	X	X		X
PROMIS (Short Form)	X	X			X
Adherence	X	X			X

(MMAS-8)					
Motivation to work	X	X			X
Employee Performance Review	X	X			X
Absenteeism Questions	X	X			X
Claim data validation with survivor				X	X
Cancer Progression Status				X	X

Schedule of events for active comparator (control) group:

Intervention or Assessment (Test)	Baseline (Day -30 to -1)	Week 1/3/5/7/9/11/13/15/17/19/21/23	Week 2/4/6/8/10/12/14/16/18/20/22/24	Month 1-6 (Every 30 days)	Month 7-18 (Every 30 days)
Async access to publically available lifestyle modification guidance		X	X		
Informed Consent	X				
Eligibility Criteria Assessment	X				
Demographic Details	X				
EHR Access Consent	X		X		X
Claims Data Access	X		X		X
QoLS (FACT-G Form)	X		X		X
Weight	X		X		X
Physical Activity	X		X		X

(GLTEQ)					
Pain (BPI-ShortForm)	X	X	X		X
PROMIS (Short Form)	X	X			X
Adherence (MMAS-8)	X	X			X
Motivation to work	X	X			X
Employee Performance Review	X	X			X
Absenteeism Questions	X	X			X
Claim data validation with survivor				X	X
Cancer Progression Status				X	X

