9.2 Analyses Supporting Primary Objective(s)

- The primary analysis will focus on quantifying the impact on total healthcare expenditure including hospitalization costs, medication expenses, outpatient visits, and any other related healthcare services over the trial period.
- We will try to establish the efficacy of Complement Theory by measuring the difference in mean total healthcare expenditure between the intervention and control groups at 3, 6, and 12 months and 18 months from baseline.
- **Statistical Model, Hypothesis, and Method of Analysis**
 - Primary Estimand (Healthcare Expenditure Reduction):
 - Null Hypothesis (H0): There is no difference in healthcare expenditure between participants in the Complement Theory program and those in the control group.
 - Alternative Hypothesis (H1): Participants in the Complement Theory program exhibit a significant reduction in healthcare expenditure compared to the control group.
 - Baseline Data Analysis: Baseline demographics and characteristics will be provided and summarized in both treatment and control groups. Standardized mean differences (SMDs) will be calculated as the measure of distance between groups. SMDs of 0.2 to <0.5, 0.5 to <0.8 and ≥ 0.8 are considered small, medium, and large, respectively. Frequencies and percentage will be provided for the binary variables as well as the

categorical variables (Yes/No); mean (standard deviation) and median (range) will be computed for continuous variables.

- Method of Analysis: A Generalized Linear Model (GLM) with an appropriate link function and distribution family that best fits the distribution of healthcare expenditure data. Both univariate and multivariate analyses will be conducted. The method will capture the effect on the outcome in treatment and control group from each independent variable. In addition, the strength of the effect from each of the variables would be evaluated through the statistical test significance, i.e., P value, at 95% confidence interval.
- **Handling of Intercurrent Events of Primary Estimand(s)**
 - For participants who discontinue the intervention or are non-adherent, we will employ a treatment policy strategy. This means all data collected will be analyzed as per the initial treatment assignment, regardless of the discontinuation or level of adherence, preserving the intention-to-treat principle.
- **Handling of Missing Data**

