 - Participants will be eligible for analysis if they have contributed a minimum amount of baseline data. The primary analyses will be based on cases with complete data. Then, multiple methods will be used to compensate for missing values in the analytical dataset.
 - An imputation rule will be assessed in such a way that if a variable has a percentage of missing values higher than a certain threshold (i.e., 50%, 70%, or 80%), then no imputation will be conducted for this variable and it may be dropped from the analytical sample to avoid an inaccurate result.
 - For intermittent missing data points, we may use LOCF, where a participant's last observed data point is carried forward to replace missing future observations.

- Multiple Imputation: For more systematically missing data, multivariate imputation by chained equation (MICE) will be used, i.e., filling the missing data multiple times based on the effect from other covariates by constructing a multivariate regression model. Multiple Imputation (MI) is superior to single imputation, as it measures the uncertainty of the missing values in a better way. The number of imputations will be 10, i.e., 10 datasets with imputed data will be created. Each imputed data set gives a point estimate of the regression coefficients as well as its standard deviation, which will be combined across the 10 datasets to obtain the final estimate of the causal RR/HR and their 95% CIs. The chained equations approach is also very flexible and can handle different variables of different data types as well as complexities such as bounds, or survey skip patterns.
- **Sensitivity Analysis**
 - To complement our intention-to-treat (ITT) analysis, a per-protocol analysis will be performed, including only participants who fully adhered to the intervention, to explore the effect of adherence on healthcare expenditure reduction.
- **Supplementary Analysis**

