9.7 Sample Size Determination

- The metric-wise sample size calculation is provided in the table below on alpha as 0.05 and power of 80% for the one-tail test at enrollment ratio = 1.

- While we are conducting the power analysis and sample size calculation based on several variables (outcomes) of interest, the sample size was computed separately for each parameter in the study and the greatest is used to obtain sample size.
- The analysis (detailed below in table) showed that sample of size of 102 is powerful enough for the analysis to cover 100% of primary and secondary metrics.
- Now since we believe that the long follow-up duration of 12 months for our trial will lead to around 30% drop-offs, we decided a final sample size of 146 (73 control, 73 test).
- So even if get 30% or 44 participants drop off we end up with final sample set of 102 (51 control, 51 test) and would be able to come to statistically significant effects ($p < 0.05$) with respect to 100% of primary and secondary metrics.

Metric Segment	Sub Metric	Control Data	Test Data	Assumed Variance	Sample Size
Primary Outcome / Concerns					
Medical Expenditure	Total Healthcare Expenditure (Planned + Unplanned)	10000	8000	Variance of 4000	102 (51 Control, 51 Test)
	No of Urgent Care Visits	3	2.5	Variance of 0.5	28 (14 Control, 14 Test)
	No of ED Visits	5	3.45	Variance of 0.8	10 (5 Control, 5 Test)
	No of unplanned outpatient/office	4.28	3.5	Variance of 0.8	28 (14 Control, 14 Test)

	visits (other than ED)				
	Unplanned Hospitalisations	5	4	Variance of 0.8	18 (9 Control, 9 Test)
	Length of hospital stay	3	2	Variance of 0.8	18 (9 Control, 9 Test)
	No of planned outpatient visits	2	1.8	Variance of 0.3	58 (29 Control, 29 Test)
	No of planned hospital visits	1.25	1	Variance of 0.1	10 (5 Control, 5 Test)
	Length of hospital stay	3	2	Variance of 0.8	18 (9 Control, 9 Test)
	Total Prescription Medicine Expenditure	1000	950	Variance of 80	80 (40 Control, 40 Test)
Secondary Outcome / Concerns					
Adherence	MMAS scale	4.5	7	Variance of 2.5	28 (14 Control, 14 Test)
QoLS Score, Pain Levels, Sleep Quality, Physical Activity	QoLS Score (FACT-G)	70	85	Variance of 20	42 (21 Control, 21 Test)
	Brief Pain Inventory (Short Form)	80	60	Variance of 35	78 (39 Control, 39 Test)

	PROMIS (Short Form)	70	55	20	46 (23 Control, 23 Test)
	GLTEQ	25	17	10	42 (21 Control, 21 Test)
	Calorie Burnt	120	198	Variance of 70	22 (11 Control, 11 Test)
Presenteeism	Attitude towards work	2	4	Variance of 1.5	16 (8 Control, 8 Test)

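### The Combined protocol and SAP permits LOCF for intermittent gaps in healthcare expenditure; carrying a value forward is not valid for a cost that accrues, though only the imputed analyses after the complete-case primary are exposed

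*Combined protocol and SAP*

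**What the plan says.** In the Combined protocol and SAP, expenditure is the primary endpoint. Section 9.2 opens: "The primary analysis will focus on quantifying the impact on total healthcare expenditure including hospitalization costs, medication expenses, outpatient visits". The estimand in Section 3, Trial Objective 1, is "The difference in mean total healthcare expenditure between the intervention and control groups over a specified period", and section 9.2 sets the comparison as the "difference in mean total healthcare expenditure between the intervention and control groups at 3, 6, and 12 months and 18 months from baseline".

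Section 9.2 then handles missing data in steps:
- Complete cases come first: "The primary analyses will be based on cases with complete data".
- Other methods follow. One is optional: "For intermittent missing data points, we may use LOCF, where a participant's last observed data point is carried forward to replace missing future observations".
- Another is firm: "For more systematically missing data, multivariate imputation by chained equation (MICE) will be used", with 10 imputations. The same bullet rates multiple imputation above single imputation.

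Section 6.1 schedules "Claims Data Access" at baseline, in even weeks to week 24, and every 30 days in months 7-18.

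Three things are not stated: whether a data point is the cost in a period or a running total, where the line falls between intermittent and more systematic missingness, and whether cost is exempt from LOCF.

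The point concerns the Combined document only. In the separate Protocol, expenditure is exploratory, section 9.2 uses MICE for FACT-G without LOCF, and LOCF appears only for presenteeism scores in section 9.3.

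**The concern.** LOCF treats the last value as a state that persists until the next observation. That can be argued for a symptom score. Expenditure is a flow that is summed, so the last recorded amount says little about what was spent during a gap.

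The error depends on an unstated choice. On the period-cost reading an admission can be billed more than once. On the running-total reading the missed time adds nothing until a later total is seen. The two readings err in different directions, and nothing tells the analyst which to use. At stake is the credibility of the imputed expenditure analyses. They carry real weight here, because section 9.7 expects about 30% drop-off and a complete-case result will need support.

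**Working it through.** **Plan's own figure.** Section 9.7 sizes expenditure "on alpha as 0.05 and power of 80% for the one-tail test at enrollment ratio = 1", with means of 10,000 and 8,000 and a spread of 4,000. Per arm, n = 2(1.645 + 0.842)² × 4,000² / 2,000² = 49.5, so 50. The t-test version gives 50.15, so 51 per arm and 102 in total, as stated. Then 102 / 0.70 = 145.7, so 146. This works only if the 4,000 labelled a variance is used as an SD. The sample size does not depend on the LOCF rule; the planned difference of 2,000 serves below as a yardstick.

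**(a) Data point = period cost.** Let routine cost be b per period, the last observed period contain a bill H, and the gap last k periods. LOCF enters k(H + b) where the truth is kb, so the excess is kH.
- H = 5,000, k = 1: excess 5,000.
- H = 8,000, k = 2: excess 16,000. That one participant moves an arm mean by 16,000/73 = 219 to 16,000/51 = 314.
- H = 20,000, k = 3: excess 60,000.

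If the last observed period held no large bill, LOCF repeats only routine cost.

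**(b) Data point = running total.** Assume 10,000 accrues evenly over 18 months (556 a month) and values exist only at the four analysis times.

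| Missed time point | True total | Value carried | Error |
|---|---|---|---|
| 6 months | 3,333 | 1,667 | -50% |
| 12 months | 6,667 | 3,333 | -50% |
| 18 months | 10,000 | 6,667 | -33% |

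A missed 3-month value likewise falls back on an earlier, lower total. After an intermittent gap the next observed total restores the cost. With running totals kept at every scheduled report, simulated intermittent gaps lower the 18-month mean by only about 0.2-0.5%.

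**(c) Data point = window cost.** The windows are 3, 3, 6 and 6 months. Carrying the months 3-6 cost into months 6-12 gives 1,667 instead of 3,333, and a total of 8,333 instead of 10,000.

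**Arm-level size for (a).** Assumptions, none from the documents except the schedule and the mean of 10,000: half the cost is routine and half is 8,000 admissions; 5% of reports are missed, rising to 30-50% just after an admission (two fortnights, or one to two monthly reports); reports are 12 fortnightly, then 12 at 30 days.

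Hand check, one monthly report affected. Fortnightly reporting covers 168 of 528 days (0.32) and monthly reporting 0.68. Expected repeats per admission:
- 30%: 0.32 × (0.30 + 0.09) + 0.68 × 0.30 = 0.33
- 50%: 0.32 × (0.50 + 0.25) + 0.68 × 0.50 = 0.58

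Subtract about 0.06 for admissions that themselves fall in a missed report. The net is 0.27 to 0.52, times 5,000 of admission cost = 1,350 to 2,600, or roughly 13-26%. This ignores admissions too near the end of follow-up to be repeated.

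Simulation on the same grid:

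| Missingness | Arm mean | Arm SD |
|---|---|---|
| 30-50% after an admission, one monthly report affected | about +13 to +23% | from about 1.4 times |
| 30-50% after an admission, two monthly reports affected | about +14 to +29% | up to about 1.8 times |
| 10% at random | about right | about +10% |

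The model's true SD is about 6,300, not the plan's 4,000, so the SD results are best read as ratios.

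**The case against.** The strongest reply is that little depends on this sentence. The primary analysis uses complete cases, LOCF is only permitted, it is confined to intermittent gaps, and the plan commits to MICE for heavier missingness. Costs come from claims and Explanation of Benefits records, so a missed report is not necessarily an unobserved cost. All of that stands, and it limits the exposure to the follow-on imputed analyses. It does not make LOCF valid there.

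Several stronger readings are tempting, and the documents do not support them:
- *That the primary expenditure estimate is itself built on LOCF.* Section 9.2 puts complete cases first.
- *That someone with no data after month 6 keeps a 6-month total at month 18.* That is dropout. It fits the MICE sentence better than the LOCF sentence, although the boundary is undefined.
- *That missed periods simply become zero cost in the final total.* With intermittent gaps in a running total, later values recover the cost.
- *That the rise in an arm's mean can be set against the planned 2,000.* Both arms get the same rule. On a simplified grid of 39 fortnights with equal missingness rules in both arms, the 2,000 contrast shifts by about 14-61%, depending on how far the effect acts through admissions. If missingness differs by arm, the shift could go either way.
- *That reports are known to be missed more often after admissions.* No section says so, and all of the mean inflation rests on that assumption.

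**Conclusion.** The concern holds for the imputed expenditure analyses in the Combined protocol and SAP. LOCF does not return the defined quantity on any reading of the data point: a period cost repeats the last bill, a running total is low at a missed 3-, 6- or 12-month time point (and at 18 months only if the last value is missing), and a window cost is carried between windows of unequal length.

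The 13-29% rise in an arm's mean and the 1.4-1.8-fold SD are conditional on the assumed cost mix and on missed reports clustering after admissions. Without that clustering, the mean is about right and the cost is precision: an SD about 10% larger at 10% missing. Neither the direction nor the size of a between-arm bias can be taken from the documents. This should be corrected before analysis, but it does not by itself undermine the complete-case primary result.

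**What to change.** In section 9.2 of the Combined protocol and SAP:
1. Delete LOCF for expenditure.
2. State that the data unit is cost per analysis window: 0-3, 3-6, 6-12 and 12-18 months.
3. Fill missed periods from the dated claims and Explanation of Benefits records where access allows. Section 11.2 recommends access for between 6 and 18 months, so recovery will not always be possible.
4. Impute windows still missing with the MICE already planned, using arm, prior-window cost and admissions as predictors, and then sum to the total.

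Imputing by service type at fortnightly level is not needed and may not be estimable with 146 participants. The cost is a few sentences in the SAP and slightly more analysis work; no new data source is required.

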9.3 Analysis Supporting Secondary Objective(s)

- **Secondary Objective 1: Adherence to Treatment**

- Statistical Model and Hypothesis:

- A composite score will be calculated to represent the adherence to treatment using the MMAS-8 survey, i.e. the average of the MMAS-8 survey score will be derived, and will be rounded to the nearest whole number.
- Model: Mixed models for repeated measures (MMRM) will be utilized to analyze changes in the composite score of adherence to treatment over time, accounting for within-subject correlations. The models allow for the inclusion of both fixed effects and random effects to account for individual variability. In addition, covariate-time interaction terms will be included to guarantee the best results. The strength of the effect from each covariate will be evaluated through the statistical test significance, i.e., P value, at 95% confidence interval.
- Hypothesis:
 - H0: There are no differences in the composite score of adherence to treatment between the intervention and control groups at specified time points during and after the intervention period.
 - H1: There is a significant difference in the mean change in the composite score of adherence to treatment between the intervention and control groups, favoring the intervention group.

- Handling of Intercurrent Events:

- Intercurrent events, such as changes in cancer treatment outside the study protocol or significant life events affecting adherence to treatment, will be documented. Participants experiencing these events will remain in the analysis as per the intention-to-treat

principle, with additional sensitivity analyses conducted to assess the impact of such events on the primary analysis.

- Handling of Missing Data:
 - Given the potential for missing data on the MMAS-8 survey due to dropout or non-response, a multiple imputation approach will be adopted before the calculation of the composite score of adherence. The imputation model will incorporate variables predictive of missingness and outcomes to generate plausible values for missing data.
- Subgroup Analysis:
 - To validate the findings from the primary analysis, subgroup analysis will be performed by excluding participants with major protocol deviations, which will provide insight into the effect of adherence to treatment outcome.
- **Secondary Objective 2: Influence on Quality of Life Score (QoLS), Pain, Sleep and Physical Activity**
 - Statistical Model and Hypothesis:
 - Model: Mixed models for repeated measures (MMRM) will be utilized to analyze changes in FACT-G scores over time, accounting for within-subject correlations. This model allows for the inclusion of both fixed effects and random effects to account for individual variability. In addition, covariate-time interaction terms will be included to guarantee the best results. The strength of the effect from each covariate will be evaluated through the statistical test significance, i.e., P value, at 95% confidence interval.
 - Hypothesis:
 - H0: There is no difference in the mean change in QoLS score, Brief Pain Inventory Score, GLTEQ score and PROMIS Score

between the intervention and control groups at specified time points during and after the intervention period.

- H1: There is a significant difference in the mean change in QoLS score, Brief Pain Inventory Score, GLTEQ score and PROMIS Score between the intervention and control groups, favoring the intervention group.

- Handling of Intercurrent Events:

- Intercurrent events, such as changes in cancer treatment outside the study protocol or significant life events affecting QoLS, Pain, Sleep and physical activity will be documented. Participants experiencing these events will remain in the analysis as per the intention-to-treat principle, with additional sensitivity analyses conducted to assess the impact of such events on the primary analysis.

- Handling of Missing Data:

- Given the potential for missing QoLS, Pain, Sleep and physical activity Data data due to dropout or non-response, a multiple imputation approach will be adopted. The imputation model will incorporate variables predictive of missingness and outcomes to generate plausible values for missing data.

- Subgroup Analysis:

- To validate the findings from the primary analysis, subgroup analysis will be performed by excluding participants with major protocol deviations, which will provide insight into the effect of adherence to the intervention on changes in QoLS scores, Brief Pain Inventory Scores, GLTEQ scores and PROMIS Scores.

- **Secondary Objective 3: Effect on Employee Absenteeism**

- Statistical Model and Hypothesis:

- Model: Generalized linear models with a Poisson distribution to compare the number of leave days between groups.

- Hypothesis: H0: No difference in the number of leave days between groups. H1: A significant reduction in leave days in the intervention group.
 - Handling of Intercurrent Events:
 - Analysis will consider any change in employment status as an intercurrent event, with a modified intention-to-treat analysis excluding participants who lose their job unrelated to health status.
 - Handling of Missing Data:
 - Worst-case scenario imputation for missing absenteeism data, assuming maximum observed absence for missing periods.
 - Sensitivity Analysis:
 - Repeating analyses with and without worst-case imputation to evaluate the impact of different missing data assumptions on the outcome.
- **Secondary Objective 4: Impact on Employee Presenteeism**
 - Statistical Model and Hypothesis:
 - Model: Mixed-effects models to analyze changes in work motivation and performance review scores over time.
 - Hypothesis: H0: No difference in changes in motivation and performance scores between groups. H1: Significant improvement in these measures in the intervention group.
 - Handling of Intercurrent Events:
 - Job changes or significant alterations in work responsibilities will be documented and explored in sensitivity analyses to understand their impact on presenteeism outcomes.
 - Handling of Missing Data:
 - LOCF for interim missing data points in motivation and performance scores, acknowledging potential limitations in this approach.
 - Sensitivity Analysis:

- Analysis excluding participants with significant job changes during the trial to assess the effect of such changes on presenteeism outcomes.

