8.2 Efficacy Assessments and Procedures

Healthcare Expenditure Reduction (Trial Objective 1):

- Endpoint: Total healthcare expenditure, including hospitalization costs, medication expenses, outpatient visits, etc.
- Assessment Procedure: Conduct comprehensive assessments of healthcare expenditure for participants in both the intervention and control groups at specified time points (e.g., baseline, 3 months, 6 months, 12 months and 18 months).
- Data Collection: Obtain detailed data on healthcare utilization, costs of medical services, medication expenses, and related healthcare expenditures through EHR access granted by participants, and participant-reported information.
- Analysis: Calculate the mean total healthcare expenditure for each group and compare the differences between the intervention and control groups over the trial period.

Impact on Adherence to Treatment (Trial Objective 2):

- Endpoints: Change in MMAS-8 scores
- Assessment Procedures: Administer the MMAS-8 questionnaire to assess adherence levels to treatment regimen at baseline and specified time points during and after the intervention period.
- Data Collection: Obtain self-reported scores from participants on adherence levels.
- Analysis: Calculate the mean difference in change in survey scores between the intervention and control groups at each time point to evaluate the impact

Improvement in Quality of Life Score (QoLS), Pain, Sleep and physical activity (Trial Objective 3):

- Endpoint: Change in FACT-G, GLTEQ, BPI-ShortForm, PROMIS scores measuring quality of life, physical activity, pain levels, and sleep
- Assessment Procedures: Administer the above four questionnaires to assess participants' at baseline and specified time points during and after the intervention period.
- Data Collection: Obtain self-reported scores from participants on Quality of Life, Pain levels, and behavior change specifically with Healthy Diet intake and ability to do physical activity.
- Analysis: Calculate the mean difference in change in scores between the intervention and control groups at each time point to evaluate the impact of the intervention.

Reduction in Employee Absenteeism (Trial Objective 4):

- Endpoint: Number of leave days taken by employed cancer survivors due to health issues.
- Assessment Procedures: Track the number of leave days (sick leave, short-term disability, long-term disability) taken by participants in both groups throughout the trial period.

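### Combined protocol and SAP, 9.3: the MMAS-8 score is averaged and rounded before analysis, without saying what is averaged, although the endpoint is defined and sized on the unrounded score

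*Combined protocol and SAP*

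**What the plan says.** All of this concerns the Combined protocol and SAP. The document titled Protocol has FACT-G as its primary endpoint and no MMAS-8 endpoint.

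- **Section 9.3, Secondary Objective 1 (derivation).** The analysed variable is a composite: "the average of the MMAS-8 survey score will be derived, and will be rounded to the nearest whole number". An MMRM is then used to "analyze changes in the composite score of adherence to treatment over time, accounting for within-subject correlations", and both hypotheses are stated on this composite. No score range, no definition of what is averaged and no reason for rounding are given.
- **Section 9.3, missing data for the same objective.** "a multiple imputation approach will be adopted before the calculation of the composite score of adherence".
- **Section 3, Trial Objective 2.** The endpoint is "Measured through change in MMAS-8 survey scores".
- **Section 8.2.** The analysis is to "Calculate the mean difference in change in survey scores between the intervention and control groups at each time point to evaluate the impact". Neither Section 3 nor Section 8.2 mentions averaging or rounding.
- **Section 9.7.** The table row reads "MMAS scale 4.5 7" (control, then test), with "Variance of 2.5" and 28 participants (14 per arm), under "alpha as 0.05 and power of 80% for the one-tail test at enrollment ratio = 1".

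The other questionnaires in Section 9.3 (FACT-G, pain, sleep, physical activity) have no rounding rule.

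**The concern.** The plan gives two descriptions of one endpoint. Sections 3, 8.2 and 9.7 work with a score on which 4.5 and 7 are possible values. Section 9.3 works with a whole number obtained by averaging something unspecified. Two analysts could follow 9.3 faithfully and derive different variables.

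The consequence depends on the reading. Placing imputation before the composite is calculated fits averaging over the survey's items, though it does not prove it. Under that reading a graded score may shrink to a yes/no variable at a cut-off that nobody chose. Precision would be lost, many real improvements would be scored as no change, and the result would be reported on a scale unrelated to the sample-size row. Under other readings little is lost, but rounding still achieves nothing.

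**Working it through.** **Inputs.** From 9.7: means 4.5 and 7, spread 2.5, one-sided alpha 0.05, power 80%, 14 per arm for this row, 51 completers per arm for the trial. Assumed, because the documents do not state them: eight items, total 0 to 8, halves rounded up.

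**1. Reproduce the plan's figure.** With 2.5 taken as a standard deviation, the effect is 2.5/2.5 = 1.00 SD.
- Normal approximation: n = 2 × (1.645 + 0.842)² / 1.00² = 12.4, so 13 per arm.
- t-test: 13.10, so 14 per arm and 28 in total, an exact match.
- With 2.5 as a true variance (SD 1.58): 5 or 6 per arm, which does not match.

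So the row uses its 2.5 as an SD despite the label, and it sizes an unrounded score.

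**2. Item-average reading: what rounding does to a score.** The item average is total/8, which lies between 0 and 1. Rounding gives 1 if the total is at least 4, otherwise 0.
- 4.5/8 = 0.5625 rounds to 1, and 7/8 = 0.875 rounds to 1. A participant going from 4.5 to 7 scores a change of 0.
- Take participants who gain exactly 2.5 points, with baselines between 0 and 5.5. A change registers only for baselines from 1.5 to just under 4. With baseline mean 4.5 and SD 2.5 that share is (0.421 − 0.115)/(0.655 − 0.036) = 0.306/0.619 = 0.49. About 51% of them show no change.

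**3. Item-average reading: the comparison between arms.** With normal scores and SD 2.5:
- Control: P(score = 1) = Φ((4.5 − 4)/2.5) = Φ(0.2) = 0.579.
- Test: P(score = 1) = Φ((7 − 4)/2.5) = Φ(1.2) = 0.885.
- Difference: 0.306, against 2.5/8 = 0.313 for the unrounded item average. The difference in means survives.
- Standardized effect: average variance (0.244 + 0.102)/2 = 0.173, SD 0.416, so 0.306/0.416 = 0.74, down from 1.00. A beta distribution on 0–8 gives 0.71.
- Required n: with mean proportion 0.732, n = [1.645 × √(2 × 0.732 × 0.268) + 0.842 × √(0.244 + 0.102)]² / 0.306² = (1.030 + 0.495)² / 0.0934 = 24.9, so 25 per arm (27 under the beta distribution), against 13–14 unrounded.
- Power at 14 per arm: Φ[(0.306 × √14 − 1.030)/0.588] = Φ(0.19) = 58% (55% beta).
- Power at 51 per arm: Φ[(0.306 × √51 − 1.030)/0.588] = Φ(1.96) = 97.5% (96.6% beta).

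**4. Simulation.** One-sided t-test, a single visit, scores truncated to 0–8, SD 2.5. Truncation pulls the means to about 4.44 and 6.43, so the simulated difference is about 2.0; the SD shrinks too, and the standardized effect stays at 0.98.

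| Setting | Unrounded | Rounded item average |
|---|---|---|
| 4.5 vs 7, 14 per arm | 81% | 56% |
| 4.5 vs 7, 51 per arm | 99.9% | about 98% |
| 4.5 vs 5.75 (half the effect, assumed), 51 per arm | 79% | 62% |

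**5. Total-score reading.** If the total itself is rounded, power at 14 per arm is 79% against 81%. Under the beta model the standardized effect is 0.99 against 1.00.

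**The case against.** The strongest reply is that the damage depends on a reading the plan does not state. Section 9.3 speaks of averaging the survey score, not its items. The item count and the 0–8 range appear nowhere. The values 4.5 and 7 in 9.7 cannot occur on a 0–1 composite, which counts against item averaging. Imputing first does not settle it, because the missingness described can mean whole missing surveys. MMAS-8 is also collected repeatedly, so the average could run over assessments, although that fits poorly with a model of change over time and no averaging window is given. This objection stands: the item-average figures are conditional.

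Three stronger inferences are tempting, and the documents do not support them.

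- **That the rounded variable cannot show the planned effect because both means round to 1.** The 4.5 and 7 are arm means, not one person's before and after, and the rule rounds scores before modelling, not arm means. With the plan's spread the between-arm difference is almost unchanged (0.306 against 0.313). What falls is precision.
- **That the trial would have only 56% power for adherence.** That figure belongs to 14 per arm. The largest row in the table sets the trial's size, and 51 completers per arm leave about 97–98% for the planned effect.
- **That the defect runs through both documents.** It is confined to the Combined protocol and SAP.

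The large reserve at 51 per arm does rest on an assumed effect of a full standard deviation. With half that effect the loss is no longer small.

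**Conclusion.** The concern holds as an inconsistent and incompletely defined endpoint. Section 9.3 states an averaging-and-rounding rule that Sections 3, 8.2 and 9.7 do not share, and no reading gives the rounding a purpose.

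Its size runs from negligible (the total is rounded: about two percentage points of power at 14 per arm) to a dichotomised score that needs nearly twice as many participants per arm (the items are averaged). In the latter case the planned 51 completers per arm absorb the loss for the planned effect, but not for one half as large. The item-average results assume eight items, a 0–8 total, 2.5 as an SD and a single-visit comparison. The halved effect is an illustration and not a planning value. Overall the impact is low to moderate, on one secondary endpoint. The ambiguity itself needs no assumption.

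**What to change.** In Section 9.3, Secondary Objective 1, delete the averaging and rounding. State that the analysed variable is change from baseline in the unrounded MMAS-8 total, on the scale used in 9.7, and give the scoring range. State that imputed values are not rounded. This brings 9.3 into line with Sections 3, 8.2 and 9.7. In the 9.7 row, relabel the 2.5 as a standard deviation, since that is how it was used.

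The cost is a sentence or two in 9.3 and one label in 9.7. No new data, visits or participants are needed, and there is no statistical downside.
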